22.10 MULTIPLICITY ADJUSTMENT

The secondary endpoints will only be tested if the primary endpoint demonstrates superiority. By pre-specifying the order in which the primary and conditional effectiveness hypotheses are performed, there is no type 1 error inflation and nominal alpha levels may be used on the primary endpoint.

Should the primary endpoint be met, the clinical response endpoint (Endpoint #1 in SAP version 2) will be tested. Should the secondary Endpoint #1 be met, the remaining endpoints will be tested using Hochberg correction for multiplicity. Complete details for multiplicity adjustment are provided in the SAP.

22.11 EVALUATION OF BLINDING

An evaluation of blinding will be performed. Prior to subjects unblinding through the system they will respond to the question "Which treatment arm do you think you are in?" (answers: sham/active), followed by the question "How certain are you of this?", with the options 1 to 5 where 5 is very certain and 1 is very uncertain. The counts and percentages of the subjects responding correctly will be tabulated and reported.

22.12 DEVICE SURVIVAL

Kaplan-Meier survival analysis will be used to characterize device failure time. Device failure in this study is defined as the device not operating as intended without unexpected failure. Unexpected failure is defined as a failure that is not related to device functionality. For example, the device accidentally falling out of a window would be categorized as an unexpected device failure. In contrast, the device failing to turn on would be considered an expected device failure. As the device is not expected to have any unexpected failures, unexpected failures will only be reported if they occur. Lifetables will be tabulated indicating the number of "failures" and the number of "at- risk" subjects over time for all failures, unexpected failures and expected failures. If there are more than one of each expected and unexpected failures, a log-rank test will be performed to compare the device failure time distribution.

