22.2 SAMPLE SIZE ASSUMPTIONS AND CALCULATIONS

The sample size calculation is based on data from Brunoni et al (2017). The calculation is based on a two- sample t-test for mean difference with the following assumptions:

- Group difference in means = 3.2
- Standard deviation of Investigational and Sham groups = 7.1 and 7.9, respectively
- One-sided type I error = 0.025
- 80% power

The resulting sample size is 176 subjects. To obtain an increase in statistical power (87.6%), 216 subjects were chosen. Accounting for 20% attrition, the overall sample size will be 270 subjects.

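### The log-rank test in section 22.12 names no comparison groups; read naturally it sets expected against unexpected failures of the same devices and cannot compare failure-time distributions as stated

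*Protocol*

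**What the plan says.** Protocol section 22.12 (Device Survival) opens with the method: "Kaplan-Meier survival analysis will be used to characterize device failure time". It then defines the event: "Device failure in this study is defined as the device not operating as intended without unexpected failure". The other kind of failure is set apart by its cause: "Unexpected failure is defined as a failure that is not related to device functionality", with a device falling out of a window as the example. For the remaining kind the section says: "In contrast, the device failing to turn on would be considered an expected device failure".

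Lifetables of failures and numbers at risk over time are planned for three categories: all failures, unexpected failures and expected failures. The test follows directly: "If there are more than one of each expected and unexpected failures, a log-rank test will be performed". Its stated purpose is to compare failure-time distributions.

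The section names no randomised arm, site or other baseline factor for this test. It states that unexpected failures are not anticipated and will be reported only if they occur. It gives no event rate, alpha or power. Sections 22.5.1, 22.6 and 22.10 refer to the SAP for detail; section 22.12 does not.

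**The concern.** A log-rank test compares event times between groups whose membership is fixed before the event, each with its own set of units at risk. Whether a failure is expected or unexpected is known only once a device has failed. Until then every device is at risk of both, and a device that never fails belongs to neither category. Failure type is therefore an outcome with two competing causes, not a grouping variable.

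The event definition adds a second difficulty. It leaves unexpected failures out of device failure, yet they are counted in the lifetable for all failures and are needed to trigger the test.

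What is at stake is the reading of one p-value in a reliability analysis. Section 24.4 says the data will support a premarket approval application, and the device is used at home. A p-value presented as a comparison of failure times, when it is not one, could be misread there.

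**Working it through.** Section 22.12 states no numerical result, so there is no figure to reproduce. The check asks what the log-rank statistic becomes under each way of carrying out the sentence.

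**Inputs.**
- From section 22.12: two failure types on the same devices, and a trigger of at least 2 failures of each type.
- From section 22.2: "Accounting for 20% attrition, the overall sample size will be 270 subjects" (216/0.8 = 270). This is a count of subjects. It is used as the number of devices for illustration only, since section 15.1 allows for replacement of a broken device.
- From sections 6 and 7: a 10-week blinded phase.
- Assumed, because the protocol gives none: failure probabilities of 2% to 10% per type over 10 weeks.

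**Version A: every device enters both curves, with the other failure type censored.** This fits the planned at-risk counts better.
1. Just before any failure, the n devices still at risk appear once in each curve, so the two risk sets are identical.
2. With no ties, each failure has expectation n/(2n) = 1/2 in the expected-failure curve and variance 1/2 × 1/2 = 1/4.
3. Summing over failures, observed minus expected = D_exp − (D_exp + D_unexp)/2 = (D_exp − D_unexp)/2, and the variance = (D_exp + D_unexp)/4.
4. Hence z = (D_exp − D_unexp)/√(D_exp + D_unexp). No failure time remains in the formula.

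Examples, whatever the weeks of failure:
- 2 versus 2: z = 0.
- 8 versus 2: z = 6/√10 = 1.90.
- 13 versus 3: z = 10/√16 = 2.50.

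Simulation with 270 devices (1,500 trials per setting, two-sided 5% level, keeping trials that met the trigger) gave the same z as this formula in every trial. Rejection rates were:

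| Expected / unexpected failure probability | Time patterns | Rejection |
|---|---|---|
| 5% / 5% | both constant hazard | 4.9% |
| 5% / 5% | very different (Weibull shapes 0.6 and 2.5) | 4.3% |
| 6% / 2% | both constant hazard | 66.0% |
| 10% / 2% | both constant hazard | 98.6% |

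The test does not respond to a large difference in timing and responds strongly to a difference in counts.

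**Version B: only failed devices enter, grouped by failure type.** Devices that never fail are dropped. At 2 versus 2, the most extreme ordering has both failures of one type first:
1. First failure: 4 at risk, 2 in the group; expectation 2/4 = 0.5, variance 0.25.
2. Second failure: 3 at risk, 1 in the group; expectation 1/3, variance 1/3 × 2/3 = 0.2222.
3. After that the group has no device left and contributes nothing.
4. Observed minus expected = 2 − 0.8333 = 1.1667; variance = 0.4722; z = 1.1667/√0.4722 = 1.70.

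There are 6 orderings, 2 of them this extreme, so the smallest exact two-sided p is 2/6 = 0.33. At 3 versus 3 it is 2/20 = 0.10. In the simulation, rejection was 6.9% to 8.2% at a nominal 5% when both hazards were constant. It was 64.5% for the two Weibull patterns. This version does react to timing, but only among devices already known to have failed, and known to have failed from that cause.

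**The definition.** Under the event definition, unexpected failures are not device failures. Under the lifetable plan, they are part of all failures. Both cannot hold for one endpoint.

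**The case against.** The strongest reply is that the section never says which groups are compared. Expected versus unexpected is inferred from the trigger and from the lifetable categories just before it, and the clause might instead be a minimum-event condition for some other grouping. That the reading is an inference stands. It does not rescue the sentence. If Active versus Sham was meant, the protocol does not say so, and requiring more than one failure of each type would serve no purpose. A SAP could supply the missing detail, but this section does not point to it.

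A reader might go further in three ways that the documents do not support.

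- *That the p-value would be meaningless.* Version A is a correctly sized test of equal cause-specific hazards (4.9% under equal constant hazards). It answers a question about counts that the section did not ask.
- *That the test discards all unfailed devices.* Only version B does so, and the planned at-risk counts point towards version A.
- *That Kaplan-Meier curves by type would seriously overstate failure.* The section splits only the lifetables explicitly by type. At an assumed 5% per type with equal constant hazards, one minus Kaplan-Meier is 5.00% against a cumulative incidence of 0.5 × (1 − 0.95²) = 4.88%. At 2% it is 2.00% against 0.5 × (1 − 0.98²) = 1.98%. Censoring a device that was dropped is also defensible when intrinsic reliability is the target.

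The reply on importance also stands. Device survival is not among the primary, secondary or exploratory endpoints in sections 11.5 to 11.7, and no decision rule depends on it.

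**Conclusion.** The point holds, at low severity. On its natural reading, the planned test treats two competing causes of failure on the same devices as if they were two independent samples. One implementation compares only the number of failures of each type. The other compares timing within groups formed by the outcome. Neither compares the failure-time distributions of two groups of devices. At the trigger minimum of 2 versus 2, neither can reach two-sided 0.05: |z| is 0 in the first and at most 1.70 in the second.

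The algebra and the 2 versus 2 result need no assumption beyond untied failure times. The rejection rates depend on the assumed failure probabilities and on 270 devices, and only illustrate the behaviour. The conclusion also rests on reading the trigger as naming the groups; on any other reading, the defect is that the groups are not named.

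No primary or secondary endpoint and no alpha is affected. Because the protocol expects no unexpected failures, the test may never be run.

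**What to change.** Delete the log-rank test between failure types. Report the number of failures of each type and the cumulative incidence of each, descriptively, with the other type as a competing event.

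If a test is wanted, state that it compares the randomised arms, Active versus Sham, and remove the condition of more than one failure of each type.

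Rewrite the definition of device failure so that it agrees with the lifetable for all failures: either it covers both types, with expected and unexpected as sub-categories, or unexpected failures are left out of the combined table.

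The cost is a change to two or three sentences in section 22.12 and a standard estimator. No additional data are needed, and the sample size and error control are unchanged.

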22.13 POOLABILITY ANALYSIS

Poolability will be assessed through stratification of the primary endpoint by Country (OUS and US). Within country point estimates will be calculated along with nominal descriptive 95% Confidence Intervals. The focus of this analysis will be on the similarity of the country specific point estimates. Differences will be described in the Clinical Study Report.

Statistical evaluation of the primary endpoint will be evaluated by adding site by treatment group term to the primary MMRM model. A p-value of ≤ 0.10 will be considered significant for this poolability assessment. Should a significant site x treatment group interaction be present, the patient factors of age, gender, and baseline scores will be assessed to understand if differences in case-mix factors explain differences observed between sites.

22.14 SAFETY ANALYSES

Assessment of the safety of the investigational device will include an evaluation of the incidence and severity of complications and adverse reactions associated with the treatment.

Adverse event rates will be summarized by type of AE and for specific AEs in two ways:

- 1. per subject incidence of specific AEs and classes of AEs and
- 2. by event, summarizing event counts by visit interval over time and in accordance with FDA Guidance (CDRH 2004)¹⁵.

Device and procedure-related events will be summarized by severity and relatedness. Events listings that include details such as relatedness, severity, onset, and resolution status will be provided for all events and relevant subsets of events such as serious events and related events. Primary safety comparisons will be performed using the AT analysis set. The summary tables will show the adverse events (in coded terms), the total number of events, and the number and the percentage of subjects affected in each treatment group

¹⁵ CDRH. Guidance for Industry and FDA Staff: Clinical Data Presentations for Orthopedic Device Applications, December 2, 2004.

("subject wise evaluation") and stratified by relation to device and severity. Data of dropouts will be presented separately, and possible bias will be discussed in the final report.

All AEs will be summarized in listings for the AT analysis set. The following AE listings will be constructed:

- AE Listing 1 All AEs Sorted by Group and Event Type
- AE Listing 2 All AEs Sorted by Group and Subject
- AE Listing 3 Serious AEs
- AE Listing 4 Severe AEs
- AE Listing 5 Device Related AEs
- AE Listing 6 Serious Device Related AEs
- AE Listing 7 Severe Device Related AEs
- AE Listing 8 Other AEs
- AE Listing 9 AEs among subjects discontinued early
- AE Listing 10 AEs among subjects who died

22.15 INTERIM ANALYSES

An interim analysis testing for futility, sample size re-estimation, and claiming study success with a sample size smaller than the maximum specified is specified. Please see the details in the Adaptive Design Report detailing all elements of this process.

23 ETHICS & PROTECTION OF HUMAN SUBJECTS

23.1 ETHICAL REVIEW

The study will be performed in accordance with the standard guidance on clinical investigations with medical devices on human subjects and recommendations guiding physicians in biomedical research involving human subjects adopted by the 18th World Medical Assembly, Helsinki, Finland, 1964 and later revisions.

The clinical investigational plan, informed consent, any other study specific study documents as required by regulations and all amendments to these study documents will be reviewed and approved by the FDA and appropriate IRB/EC before enrollment of any patient. In addition, the sponsor will keep the regulatory authorities informed of any SAEs throughout the study course, if applicable.

23.2 REGULATORY CONSIDERATIONS

This study will be conducted in accordance with the Good Clinical Practice (GCP) guidelines and other applicable regulatory requirements including but not limited to:

- FDA Regulations on Investigational Device Exemption (21 CFR 812)
- FDA Regulations on research with human beings (21 CFR 50, 54 and 56)
- Health and Human Services (DHHS) Regulations on research with human beings (45 CFR 46 Subparts A, B, C, and D)

- International Conference on Harmonization (ICH) Guidance for Industry-E6 Good Clinical Practice: Consolidated Guideline
- The Declaration of Helsinki

23.3 STUDY AMENDMENTS

All changes to the protocol that impact validity of data, scientific soundness, the rights safety, or welfare of the participants, must be documented in the format of an amendment with justification statements in the cover letter to the IRB/EC and FDA. All amendments must be submitted to the IRB/EC and regulatory authority for review and approval. Following approval, the protocol amendment will be distributed to all protocol recipients at each investigational site.

23.4 INSURANCE

The Sponsor has issued clinical trial insurance with appropriate coverage for the continuation of the entire study.

24 DATA HANDLING AND RECORDKEEPING

24.1 EDC AND ECRFS

eCRFs will be completed in a 21 CFR Part 11 compliant electronic data capture (EDC) system for each patient enrolled into the clinical study. The study coordinator will enter the source data onto the eCRFs, and study monitors will verify that the source documents match the eCRFs. Once verified, the study monitor will lock the field via a monitoring approval step so the data cannot be changed unless requested.

All procedures for the handling and analysis of data will be conducted using good clinical data management practices within systems meeting FDA guidelines for the handling, storage, and analysis of data for clinical studies.

The Investigator will sign off on the Eligibility Criteria, all Adverse Event, Protocol Deviation and Study Completion eCRFs and will sign each patient's casebook once the patient completes the study to attest that all data entered on the eCRFs are complete and accurate. All of the above signatures will be completed digitally within the EDC system using the system's Part 11 compliant digital signature system function.

Any required data clarifications will be handled within the EDC system's query management system. The EDC will be programmed to automatically place data clarification queries on missing values and values out of acceptable ranges. Study monitors and data managers will also be able to add data clarification queries to data points within the system. Study coordinators will have the opportunity to correct data and/or respond to the query for review by monitors and data managers.

24.2 CAPTURE OF PATIENT REPORTED OUTCOMES

Patient reported outcomes (PROs) will be collected via the participant's personal smartphone or other device running Android 5.0+ or iOS 12+ and the data will be transmitted directly into the EDC. As the data is originated in the participant's device, it is considered to be electronic source and the data is automatically locked as soon as it enters the EDC to ensure that it is secure.

24.3 STUDY RECORDS RETENTION

The Investigator and the Sponsor will maintain accurate, complete, and current records relating to participation in this clinical investigation. If the Investigator wishes to assign the responsibility of maintaining the study files to someone else or move them to another location, he/she should consult with the study sponsor in writing regarding the change. The Investigator will take measures to ensure that these essential documents are not accidentally damaged or destroyed.

Upon study completion, the study files must be maintained in a known location for a maximum of a 2 years following the date a marketing application is approved for the medical device for the indication for which it is being investigated; or, if no application is to be filed or if the application is not approved for such indication, until 2 years after the investigation is discontinued and FDA is notified.

The Investigator and Sponsor will maintain records in accordance with 21 CFR 812, Subpart G, to include:

- Current and past versions of the IRB/EC-approved clinical protocol and amendments and corresponding IRB/EC-approved consent form(s) and, if applicable, participant recruitment advertisements
- FDA correspondence related to the IDE application; including supplemental IDE applications, current investigator lists, progress reports
- IRB/EC correspondence (including submissions and approval notifications) including safety and protocol deviation reports, and annual or interim reports
- Signed Clinical Trial Agreement
- Signed Investigator Agreements and financial disclosure forms for participating Investigators
- Curriculum vitae (Investigator and Sub-Investigators)
- Certificates of required training for Investigators and Sub-Investigators, including human subject protection and Good Clinical Practice
- Instructions for handling the investigational device and other study-related materials
- Device tracking logs
- Signed ICFs

- eCRF and Source Documents
- Monitoring visit confirmation and follow-up letters
- Copies of relevant Sponsor-Investigator correspondence, including notifications of adverse event information
- Screening and Enrollment Log
- Signed informed consent forms
- Final clinical study report

24.4 PUBLICATION AND DATA SHARING POLICY

Data generated from the conduct of this study will be used to support an application by Flow Neuroscience AB as an original Premarket Approval (PMA) from FDA. Publication of the results of the study will follow Flow Neuroscience AB 's Publication and Presentation Policy.

24.5 PARTICIPANT AND DATA CONFIDENTIALITY

Participant confidentiality will be maintained throughout the study in a way that ensures that data can always be tracked back to the source data. For this purpose, a unique participant identification code (two-digit site identification number and three-digit participant name identification number code assigned sequentially) will be used that allows identification of all data reported for each participant without traceability back to the actual participant.

The Principal Investigator or institution shall provide direct access to source data during and after the clinical investigation for monitoring, auditing, IRB/EC review and regulatory authority inspections.

For investigational sites within the United States, "Protected Health Information" will be treated and maintained in compliance with the Health Insurance Portability and Accountability Act of 1996 (HIPAA) Privacy rule.

The duration of storage time of personal data at the investigational sites will be in accordance with national regulations. Electronic Case Report Form (eCRF) data captured and maintained in Curebase for each participant. Curebase stores all data in a secure cloud server of Amazon Web Services (AWS) and complies with most of HIPAA and GDPR standards, including but not limited to: password protection, platform encryption, and 2-factor verification. Curebase takes as much action as possible to maximize the protection and security of subjects' sensitive information. All data pertaining to a clinical study, including protected health information (PHI), will be retained for the duration of the study, and for 2 years thereafter, in compliance with FDA monitoring obligations. At this point, the identifiable PHI obtained during the study will be deleted. Curebase will share pseudonymized data collected from subjects with authorized representatives.

After 2 years have elapsed since the completion of a clinical investigation, Curebase will retain a de-identified version of the data obtained during that study. Curebase may retain this data

indefinitely and may use it for a variety of purposes that will include, but not be limited to, making improvements to the Curebase product.

Information obtained while executing this study, including still and motion photography, may be presented for regulatory, clinical, or educational purposes if no participant is identified. The data collected is the property of Flow Neuroscience AB.

24.6 INVESTIGATOR RECORDS

The investigator is responsible for the preparation and retention of the records cited below. All these records, except for participant's case history records, should be filed in the Investigator Site File.

24.7 PARTICIPANT RECORDS

- All Source Documentation Worksheets
- Supporting data (e.g., medical records, clinic charts)
- 24.8 INVESTIGATOR RECORDS AND REPORTS

The investigator is responsible for the timely preparation and submission of the reports cited below.

Report	Sent To	Timing of Report
Unanticipated adverse device effect (UADE) Withdrawal of IRB/EC approval	Flow Neuroscience AB, IRB/EC Flow Neuroscience AB	UADE must be reported as soon as possible, but in no event later than 10 business days after the investigator first learns of the event Reported within 5 business days
Progress reports	Flow Neuroscience AB, IRB/EC	Reported as requested by Flow Neuroscience AB or the reviewing IRB/EC, but at least yearly
Deviations from the investigation plan	Flow Neuroscience AB, IRB/EC (FDA)	A deviation to protect the life or physical well-being of a participant in an emergency must be reported no later than 5 business days after the emergency occurred. Deviations that may affect the scientific soundness of the investigational plan or the rights, safety, or welfare of the participant (and are not an emergency) must receive prior approval by Flow Neuroscience AB and be reported to the FDA and IRB/ECs.
Device use without informed consent	Flow Neuroscience AB, IRB/EC	This deviation must be reported within 5 business days after the use occurs.

Table 5: Investigator Reports

Final Report	Flow	This report must be submitted within 3 months after
	Neuroscience	termination or completion of the investigation or the
	AB, IRB/EC	investigator's part of the investigation.
Other	FDA, IRB/EC	Upon request, accurate, complete, and current
		information about any aspect of the investigation must be
		reported.
